## 8.1 SOURCE DATA DOCUMENTATION

The study database will be used to document all data collection which will include consent forms, patient questionnaires, case report forms and information about participant study visits. All patient-related data will be recorded in an pseudonymised way. Each patient will be unequivocally identified by a trial subject number, attributed at recruitment into the study. Key data from blood results, echocardiography and MRI reports will be documented in the study database. The original reports and images will be retained by the imaging core laboratory for future reference.

## **9 DATA MANAGEMENT**

### **9.1 DATA STORAGE**

Patient NHS electronic records will be accessed following formal and explicit patient consent. Pseudonymised data will be made available for other researchers to use where appropriate.

All identifiable participant information (name, age, sex, address and postcode, CHI number, telephone number, email address, height, weight, clinical condition, date of study enrolment and dates of MRI scan) will be stored in a secure manner accessible only to members of the research team on an NHS Lothian device. CHI number is required to review participants relevant medical history, medications, medical imaging and standard of care intervention results. This will be stored in a password protected Excel file on an NHS Lothian device.

All NHS Lothian computers used in the study will be encrypted, and password protected. Electronic data will be stored on (2-step) password-protected computers and only accessible to the study investigators. No personal identifiable information including CHI numbers will be accessed by members outside the research team or NHS Lothian.

Only study subject number will be transferred to the password protected University laptop.

The study will be guided by the principles of Good Clinical Practice and Data Protection Act in ensuring the confidentiality of personal data. Participant consent forms will contain personal data and a linked participant identification number. Hard copies of consent forms will be stored in a secure filing cabinet in a locked University Office ([name]). Study data will be kept on university password protected computers as linked anonymised data. This will enable the identification of each participant's data during the study, for any participant to withdraw and have personal data destroyed if they wish. All data will be anonymised after the study period.

### **9.2 PERSONAL DATA**

The following personal data will be collected as part of the research:

- Name, age, sex, address and postcode, CHI number, height, weight, clinical condition, date of study enrolment and date of MRI scan
- Personal data will be stored or accessed for a period of 6 to 12 months after the study has ended on a password protected Excel file to

allow participants to be identified so we can follow up on their management and clinical course. Thereafter, pseudonymised data may be stored for a period of up to five years.

### **9.3 DATA INFORMATION FLOW**

Patient's initials, name, signature, age and date of birth will be on the consent form which will be kept in locked cupboards in the clinical research facility. This will be pseudonymised with a unique patient code, and this will be stored on a password-protected Excel document.

### **9.4 EXTERNAL TRANSFER OF DATA**

Data collected or generated by the study could potentially be transferred to any external individuals or organisations outside of the Sponsoring organisation(s) in a fully pseudonymised or linked pseudonymised format. With consent, anonymised data collected may be shared with other academic or commercial institutions.

### **9.5 DATA CONTROLLER**

A data controller is an organisation that determines the purposes for which, and the manner in which, any personal data are processed. The University of Edinburgh and NHS Lothian are joint data controllers along with any other entities involved in delivering the study that may be a data controller in accordance with applicable laws (e.g. the site).

### **9.6 DATA BREACHES**

Any data breaches will be reported to the University of Edinburgh ([contact]) and NHS Lothian ([contact]) Data Protection Officers who will onward report to the relevant authority according to the appropriate timelines if required.

## **10 STATISTICS AND DATA ANALYSIS**

### **10.1 SAMPLE SIZE CALCULATION**

In our prior study of manganese-enhanced magnetic resonance imaging in patients with takotsubo cardiomyopathy, we observed that manganese uptake was markedly suppressed during initial hospital admission ( $5.1 \pm 0.5$  mL/100 g of tissue/min) and this partially recovered after 3 or more months ( $6.6 \pm 0.5$  mL/100 g of tissue/min) but remained below that observed in matched healthy volunteers ( $8.2 \pm 1.1$  mL/100 g of tissue/min;  $P < 0.001$ ) [Singh et al, 2022]. For study 1, this gives a 100% power to detect a similar difference between healthy

volunteers and patients not receiving any treatment (n=10) at both baseline and 3 months. In terms of treatment effects for studies 1 and 2, we anticipate an improvement of at least 0.6 mL/100 g of tissue/min which equates to just over a third of the difference between healthy volunteers and patients beyond 3 months (8.2 versus 6.6 mL/100 g of tissue/min). At 90% power and 2-sided  $P < 0.05$  this requires a sample size of 18 per group. To account for some, drop out, we have increased the number of healthy volunteers recruited to a sample size of 20. For study 2, we are exploring novel therapies with uncertain impact, but the detectable effect size will be much smaller (approximately half) given the paired comparisons, cross-over methodology and effective group sizes of 40.

## 10.2 PROPOSED ANALYSES

### 10.2.1 Imaging Analysis

Pseudonymised participant MRI data will be sent electronically to the University of Edinburgh for analysis. The first MRI scan will serve as a baseline for comparison, and the pre-contrast imaging will serve as control for each scan individually. Images will be analysed using commercially available cardiac MRI software (Circle Cardiovascular Imaging software, cvi42®, Circle Cardiovascular Imaging Inc. Calgary, Alberta, Canada) through which myocardial contouring and T1 map creation and analysis is performed.

Analysis will be performed in the Image Analysis Core of the Edinburgh Imaging facilities. A standardised approach to T1 image analysis will be employed for manganese uptake [Singh et al, 2022]. Briefly, the basal, mid-cavity, and long axis T1 maps will be divided into segments according to the standard 17-segment model recommended by the American College of Cardiology/American Heart Association [Cerqueira et al, 2002]. After contouring epi- and endocardial borders and defining right ventricular insertion points, regions of interest will be derived for each of the 16 segments with a 10-20% epi- and endocardial offset to reduce risk of blood pool contamination. Manganese uptake will be quantified using a two-compartment Patlak model as described previously [Singh et al, 2022b], and this has excellent repeatability and reproducibility [Singh et al, 2023]. All image analysis will be performed blinded to group, timing and treatment allocation.

### 10.2.2 Statistical Analysis

Summary data will be presented as number and percentage, mean  $\pm$  standard deviation or median and interquartile range as appropriate. Based on our prior data, we anticipate that the data will be normally distributed. Within group and between group comparisons will be made with paired or unpaired Student's *t*-test or analysis of variance as appropriate. For study 2, we will explore whether there is any evidence of a time-order effect before proceeding to pool the data from all participants. This will greatly enhance our power to detect

meaningful differences. Repeated measures will be assessed by analysis of variance. Statistical significance will be taken as a two-sided  $P < 0.05$ .

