#### 4.1.2 Study 2: Patients with Prior Takotsubo Cardiomyopathy

We will recruit 40 patients with prior takotsubo cardiomyopathy (>6 months previously) for this second cohort of patients. We will recruit these patients contemporaneous with Study 1 so that we can use the same 20 age and sex matched healthy volunteers as a comparator.

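### Equal-variance tests are specified although the planning SDs are 1.1 (volunteers) and 0.5 (patients): the 20 v 40 Study 2 comparison would run at about 12%, and section 10.1 misstates two sample-size details

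*Protocol*

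**What the plan says.** Section 10.2.2 of the protocol expects normally distributed data and states that "between group comparisons will be made with paired or unpaired" Student's t-tests or ANOVA, as appropriate, at two-sided P < 0.05. No unequal-variance form is named.

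Section 10.1 gives the planning data for manganese uptake in mL/100 g/min: 5.1 (SD 0.5) in patients at admission and 6.6 (SD 0.5) at 3 months or later. The latter "remained below that observed in matched healthy volunteers", who had 8.2 (SD 1.1).

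Section 4.1.2 recruits 40 Study 2 patients alongside Study 1 so that "we can use the same 20 age and sex matched healthy volunteers as a comparator".

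On group sizes, section 10.1 claims 100% power for volunteers against "patients not receiving any treatment (n=10) at both baseline and 3 months". It then sizes the treatment effect of 0.6 at 18 per group for 90% power and, for dropout, says "we have increased the number of healthy volunteers recruited to a sample size of 20". Sections 4.1.1 and 6.1.2 provide 60 Study 1 patients randomised 1:1:1.

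**The concern.** Student's t-test and ordinary ANOVA assume one common variance. The protocol's own SDs imply a variance ratio of 1.21/0.25 = 4.8. When the more variable group is also the smaller one, the pooled standard error is too small and the test rejects too often. Twenty volunteers against 40 Study 2 patients is that arrangement. At stake is whether a statement that uptake in prior takotsubo still differs from normal, or no longer does, carries its nominal error rate.

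A second route leads to the same problem. If volunteers and the three Study 1 arms share one ANOVA error term, the volunteers' variance enters the comparison of the drugs, and the patients' smaller variance enters the comparison with volunteers.

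The sample-size text has two slips of its own. The untreated group is given as 10 where the design gives 20. The dropout allowance is attached to the volunteers, who take no part in the treatment comparison that the 18 per group was calculated for.

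**Working it through.** **Inputs.** Section 10.1: SD 1.1 (volunteers) and 0.5 (patients); gaps 8.2 - 6.6 = 1.6 and 8.2 - 5.1 = 3.1; treatment effect 0.6. Sections 4.1.1, 4.1.2 and 6.1.2: 20 volunteers, 40 Study 2 patients, and 60/3 = 20 per Study 1 arm. Section 10.2.2: two-sided 5%. Rejection rates come from simulation of normal data with 400,000 replicates per case.

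**The plan's own figures.** With 20 volunteers and 10 untreated patients, power is 100% for the gap of 3.1. For 1.6 it is 99.7% (pooled) or 99.95% (Welch). The stated 100% therefore reproduces to rounding. With 20 untreated patients it is 100% and 99.99%. For the 0.6 effect, SD 0.5 needs 15 per group (normal formula) or 16 (t), and SD 0.55 gives 18 (normal formula). The stated 18 is thus of the right order; section 10.1 does not say which SD it used.

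**20 volunteers v 40 Study 2 patients.**
- Pooled variance = (19 × 1.21 + 39 × 0.25)/58 = 32.74/58 = 0.564.
- Pooled SE = √(0.564 × (1/20 + 1/40)) = 0.206.
- True SE = √(1.21/20 + 0.25/40) = 0.258.
- Ratio = 0.206/0.258 = 0.80, so the pooled standard error is about 20% too small.
- Simulated type I error: Student 11.9-12.0%, Welch 5.0%. With the volunteer SD varied from 0.9 to 1.3, Student gives 10-13%.

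**20 volunteers v one Study 1 arm of 20.** With equal group sizes, the pooled SE and the true SE are both √((1.21 + 0.25)/20) = 0.270. Simulated type I error for Student is 5.2%.

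**Volunteers and three Study 1 arms in one ANOVA (20 each).**
- Error variance = (19 × 1.21 + 57 × 0.25)/76 = 37.24/76 = 0.49, so SD 0.70 in place of 0.50 for the arms.
- SE used for any pair = 0.70 × √(2/20) = 0.221.
- Volunteer v untreated: true SE 0.270. The contrast runs at about 11%.
- Between randomised arms: true SE = 0.50 × √(2/20) = 0.158. Power for 0.6 falls from 96% to about 84%.

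**Sensitivity to the patient SD.** Type I error concerns patients whose mean equals that of the volunteers, and the protocol gives no patient SD at that level. Assuming 0.8, midway between 0.5 and 1.1, the 20 v 40 pooled variance is (22.99 + 39 × 0.64)/58 = 0.827. The pooled SE is then 0.249 against a true 0.277, and the simulated rate is about 7.7%. At 1.1 the two standard errors coincide and the test holds 5%.

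**The case against.** The strongest objection is that the wording of section 10.2.2 is generic, and that the unequal-variance form is a detail an analysis plan may supply. This stands only in part. The phrase 'as appropriate' chooses among the tests named, and all the between-group options named pool variances. The protocol has stated a method that sits badly with its own planning SDs.

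Several points on the other side do stand:
- The null case assumes that patients with normal uptake keep SD 0.5, which was observed at means of 5.1 and 6.6. If spread grows with the mean, the inflation shrinks. The protocol also gives no sample sizes for the planning SDs.
- Gaps of 1.6 and 3.1 are detected almost surely by either test.
- No listed primary, secondary or exploratory endpoint is framed as a comparison with volunteers.

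Three stronger readings are tempting, and the protocol does not support them:
- A reader might infer that every volunteer comparison is inflated, by as much as 17%. That figure (16.6%) needs all 60 acute patients pooled against 20 volunteers, an analysis stated nowhere. Against any single Study 1 arm, the stand-alone t-test runs at 5.2%.
- A reader might take the joint ANOVA as planned. Section 10.2.2 permits it but does not say that volunteers enter it.
- A reader might take n=10 as an intended analysis size that threatens power. It is an input to one power statement. Nothing else suggests that only 10 patients go untreated, and 60 randomised 1:1:1 already gives each arm 20, so the arms have the dropout margin even though the sentence names the volunteers.

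**Conclusion.** The point holds within limits. For the 20 v 40 comparison set up in section 4.1.2, the specified equal-variance test would run at about 12% where 5% is intended, provided the planning SDs carry over and patients near normal uptake keep SD 0.5. Welch's test holds 5%. The damage falls on near-null contrasts, such as whether uptake has returned to normal, and on the width of any interval reported against volunteers. Detection of the large expected gaps is not at risk. The joint-ANOVA figures (about 11%, and 96% to about 84%) are conditional on an analysis that the text leaves open.

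The untreated n=10 and the placement of the dropout allowance are real errors in section 10.1, but they are editorial and leave the stated power of about 100% unchanged.

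**What to change.** In section 10.2.2, specify Welch's t-test, or a model with group-specific variances, for every comparison with healthy volunteers. State that volunteers are left out of the ANOVA that compares the randomised arms.

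In section 10.1, replace the untreated n=10 by the 20 that follows from 60 patients randomised 1:1:1. State the increase from 18 to 20 for the randomised arms and not for the volunteers alone.

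All of this is wording. It needs no further patients, scans or data. Using Welch's test costs essentially no power: for the 1.6 gap at 20 v 40, power exceeds 99.9% with either test.

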#### 6.1.2 Doses and treatment regimens

Patients in study 1 will be randomised 1:1:1 to no treatment, or open-label valsartan or bisoprolol.

Patients in study 2 will receive 3 months treatment with combination sacubitril and valsartan and dapagliflozin 10 mg in random order. This will be separated by a one-month medication “wash out period.”

Medications will be prescribed on a research specific prescription form by a co-investigator in the Clinical Research Facility. The medication will then be dispensed “off the shelf” from the Royal Infirmary of Edinburgh pharmacy department.

Randomisation will take place by block randomisation. An unbiased colleague will create the blocks for randomisation and the study investigators will be blinded to the blocks until the point of randomisation.

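### Study 2 lets a preliminary look for a time-order effect decide whether the crossover data are pooled, without stating the test, threshold or fallback; one period-adjusted analysis of all participants should be fixed instead

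*Protocol*

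**What the plan says.** Study 2 gives each participant sacubitril/valsartan and dapagliflozin for three months each, in random order. On the interval between them, section 6.1.2 says: "This will be separated by a one-month medication" washout.

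Section 10.2.2 sets the order of the analysis: "For study 2, we will explore whether there is any evidence of a time-order effect before proceeding to pool the data from all participants". It then says that pooling will greatly increase power. The methods named are paired or unpaired t-tests or analysis of variance, as appropriate, at a two-sided 5% level. The section does not say what a time-order effect is, how it will be tested, at what level, or what will be analysed if one is found.

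Section 10.1 takes pooling for granted. After the parallel-group calculation it says that for Study 2 "the detectable effect size will be much smaller (approximately half) given the paired comparisons, cross-over methodology and effective group sizes of 40".

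The Study 2 table in section 7.2 schedules manganese MRI at screening, 3±1 months and 7±1 months. There is no scan at the 4±1 month visit, where period 2 begins.

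**The concern.** The sentence puts a look at the outcome data ahead of the choice of analysis. An SAP might supply a test and a threshold, but the protocol itself has already fixed the conditional structure, and that structure is the problem.

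The gate has two natural readings.

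- **Carry-over.** The check compares participants' two-period totals between sequences. This is a between-person test with low power. It is also strongly correlated with the period-1 comparison, the usual fallback. A chance imbalance that trips the gate therefore tends to make period 1 look significant too.
- **Period effect.** The check is not needed, because period can simply be a term in the model.

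On the first reading the error rate and the precision claimed in section 10.1 are both at stake. On either reading, the choice of which data produce the Study 2 result stays open until the data have been seen.

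**Working it through.** **Inputs from the protocol.** Two-sided 5% level (10.2.2). 90% power, difference 0.6, 18 per group, and uptake 6.6 ± 0.5 mL/100 g/min in patients at 3 or more months (10.1). 40 participants in Study 2 (4.1.2).

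**Assumed, because not stated.** SD 0.5 in each period; 20 participants per sequence; within-person correlation ρ from 0.3 to 0.8; pre-test at 5% (10% as a check); fallback to the period-1 comparison. Baseline is ignored at first.

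**1. The plan's own figures.** For a difference of 0.6 with SD 0.5, the two-sample calculation gives 15 per group (normal) or 16 (t). The stated 18 corresponds to an SD of about 0.53-0.55, so the figure is reproduced closely enough. For Study 2, half of 0.6 is 0.3. The SD of a within-person difference is 0.5 × √(2(1−ρ)). With n = 40 and 90% power, the detectable difference is 0.30 at ρ = 0.35 and 0.26 at ρ = 0.5. The claim in 10.1 is therefore consistent with a low to moderate correlation, provided that all 40 are pooled.

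**2. Carry-over reading.** The tests are two-sample t-tests between sequences on period sums (pre-test), on period differences (crossover test) and on period 1 (fallback). The correlation between the pre-test contrast and the period-1 contrast is (1+ρ)/√(2(1+ρ)) = √((1+ρ)/2), which is 0.87 at ρ = 0.5. The crossover contrast is independent of the sums. With no treatment effect and no carry-over, the overall error is therefore

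0.95 × 0.05 + 0.05 × P(period 1 significant | pre-test significant).

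At ρ = 0.5 the conditional probability simulates at 0.52, giving 0.0475 + 0.026 = 0.074.

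Simulation results (60,000 trials per setting without carry-over, 40,000 with):

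| ρ | Type I error, 5% pre-test | Type I error, 10% pre-test | Period 1 falsely significant after failed 5% pre-test | 5% pre-test power, carry-over 0.3 | 5% pre-test power, carry-over 0.6 |
|---|---|---|---|---|---|
| 0.3 | 6.9% | 7.7% | 42% | 21% | 63% |
| 0.5 | 7.4% | 8.3% | 52% | 19% | 58% |
| 0.7 | 8.0% | 8.7% | 63% | 17% | 52% |
| 0.8 | 8.2% | 9.1% | 70% | 16% | 50% |

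The crossover test without a gate held about 5% throughout. With a carry-over of 0.3 and no treatment difference, the ungated test rejects in 34-83% of trials, and the gated procedure still rejects in 30-72% (5% pre-test). The gate removes little of that bias.

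**3. Cost of the fallback.** Period 1 alone compares 20 with 20. The standard error is 0.5 × √(2/20) = 0.158 and the 90%-power detectable difference is 0.53. The pooled crossover gives 0.26-0.30 at ρ = 0.35-0.5.

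**4. Period-effect reading.** In a balanced design the period contrast is orthogonal to the treatment contrast. With a 5% period pre-test, the simulated overall error was 4.8-5.3% for ρ from 0.35 to 0.8. The remaining cost falls on an unadjusted paired t-test. A period effect π widens the SD of the differences to √(SD² + π²). At ρ = 0.5 the SD is 0.50, which becomes 0.54 for π = 0.2 and 0.71 for π = 0.5. Power for a true difference of 0.2 falls from 69% to about 63% or 37% respectively; with a period term it stays at 69%. These values of π are illustrative, since the protocol gives none.

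**5. Washout.** Taken as independent tolerances, stopping at 3±1 months and restarting at 4±1 months allows up to 5 − 2 = 3 months off drug and, at the other end (3 − 4 < 0), no gap at all. Section 6.1.2 says one month.

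**The case against.** The strongest objection is that the two-stage procedure is read into the text. Section 10.2.2 says only that the effect will be explored. A reader might infer that the plan's error rate is inflated outright. The document does not support that: inflation needs a carry-over test, a threshold and a period-1 fallback, and none is stated. On the period reading the inflation vanishes. This stands, and the 7-8% is accordingly conditional.

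A reader might also infer that the pre-test cannot detect carry-over. That goes too far: power is 50-63% for a carry-over of 0.6, the improvement anticipated in 10.1. Little power is the accurate description.

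The baseline scan also softens the figures. With baseline-adjusted tests and equal correlation among the three scans, type I error is 6.8-7.2%, period 1 is falsely significant after a failed pre-test in 45-50% of trials, detection of a 0.3 carry-over is 24-44%, and the period-1 detectable difference is 0.49 down to 0.32. The problem shrinks but does not disappear.

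Analysis of variance is among the named methods and could include period, so an unadjusted paired t-test is not certain. Finally, the ±1 month figures may be no more than visit tolerances around a fixed one-month washout. The overlap does not show that the washout will be too short and is not evidence about the pre-test; it is a separate point to clarify.

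**Conclusion.** The concern holds in a conditional form. Section 10.2.2 makes pooling follow a look at the same data, while section 10.1 counts on pooling all 40, and the gate helps on neither reading. As a carry-over test with a period-1 fallback, it raises the type I error by about 2 to 3 percentage points, offers weak protection, and when triggered gives up most of the crossover's precision. As a period test it is harmless to the error rate but redundant. The figures rest on SD 0.5, 20 per sequence, the assumed correlations, a 5% pre-test and, except where stated, no baseline adjustment. The protocol does not settle which reading is meant, and that should be closed before Study 2 data are analysed.

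**What to change.** - Delete the conditional step in section 10.2.2. State that all Study 2 participants will be analysed together whatever any order assessment shows.
- Prespecify one linear mixed model with treatment and period as fixed effects and participant as a random effect, including participants who complete one period only.
- State how the single baseline scan enters, both for the comparison between drugs and for any comparison of each drug with baseline.
- Report any sequence or carry-over estimate descriptively, with its confidence interval, and state that it does not change the primary analysis. Rest the assumption of no relevant carry-over on the washout, since no scan at the start of period 2 allows it to be checked on the primary endpoint.
- Separately, reconcile the one-month washout in section 6.1.2 with the 3±1 and 4±1 month windows in the Study 2 table of section 7.2.

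The cost is protocol and SAP wording. No added participants, scans or visits are needed.

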## **5.3 WITHDRAWAL OF STUDY PARTICIPANTS**

Participants are free to withdraw from the study at any point or a participant can be withdrawn by the Investigator. If withdrawal occurs, the primary reason for withdrawal will be documented if possible. The participant will have the option of withdrawal from all aspects of the study but continued use of data collected up to that point. To safeguard rights, the minimum personally identifiable information possible will be collected. If participants withdraw from the study, they will not need to be replaced.

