### 6.4.1 Procedures for discontinuation of a subject from study medication

Brief interruptions of therapy will be permitted (<14 days) where there is a clinical need. If medication needs to be stopped for longer than 14 days then the patient will be withdrawn from the study. This will be documented in patients' medical records. Reasons for interruption or discontinuation of study medications include side effects of medications. The table below summarises some side effects associated with the study medication:

Study Medication	Potential side effects
Bisoprolol	Hypotension, bradycardia, erectile dysfunction, rash, cold peripheries
Valsartan	Hypotension, impaired renal function, nausea, diarrhoea, rash
Sacubitril/Valsartan	Hypotension, impaired renal function, nausea, diarrhoea, rash
Dapagliflozin	Diabetic ketoacidosis, genital infections (only applies to patients with type 2 diabetes mellitus)

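### Study 1 and Study 2 scans are to be analysed by ANOVA and t-tests, which use incomplete scan records poorly, although the withdrawal rule can remove only treated patients in Study 1; a mixed model on all scans is better, with a modest gain that depends on missing at random

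*Protocol*

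**What the plan says.** Section 10.2.2 names the methods. For repeated scans: "Repeated measures will be assessed by analysis of variance". For the rest: "Within group and between group comparisons will be made with paired or unpaired Student's" t-test, or analysis of variance, as appropriate. It names no model that keeps partial records.

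Section 7.2 schedules three manganese scans per patient: screening, 4 weeks and 3 months in Study 1; screening, 3 months and 7 months in Study 2.

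Section 6.4.1 sets the withdrawal rule: "If medication needs to be stopped for longer than 14 days then the patient will be withdrawn from the study". Section 6.1.2 randomises Study 1 patients 1:1:1 to no treatment, valsartan or bisoprolol, and gives every Study 2 patient both treatments in random order.

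Section 5.3 adds: "If participants withdraw from the study, they will not need to be replaced". It also allows data gathered before withdrawal to be kept, so earlier scans are available to an analysis that can use them.

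**The concern.** Three rules interact. The method named for repeated scans needs complete records, withdrawals are not made good, and one cause of withdrawal cannot occur in the untreated arm of Study 1. The patients with a 3-month scan in a treated arm may therefore be a selected group, set against an untreated arm that is not selected in this way. If those lost had lower uptake, the comparison would favour the drug.

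Section 6.4.1 gives side effects as a reason for interrupting or stopping drug, and section 7.2 has dose-adjustment visits at weeks 1 and 2, so some loss of this kind is foreseeable. In Study 2 everyone takes both treatments. There the rule has no treated-versus-untreated asymmetry; its cost is patients with only one of the two treatment scans.

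**Working it through.** **Inputs from the protocol.** Section 10.1: effect 0.6 mL/100 g/min, SD 0.5 in patients at 3 months or more, power 90%, two-sided 0.05, 18 per group. Section 4.1.1: 60 patients in Study 1, so 60/3 = 20 per arm. Section 4.1.2: 40 patients in Study 2. **Assumed**, because the protocol gives no value: rates of loss, and correlation 0.3-0.7 between a patient's scans.

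**1. The plan's own figure.** n = 2(1.96 + 1.2816)² SD²/0.6² per group.
- SD 0.5: 21.015 × 0.25/0.36 = 14.6, so 15 (16 by the exact t calculation).
- SD 0.55: 21.015 × 0.3025/0.36 = 17.7, so 18.

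The stated 18 is reproduced at an SD slightly above 0.5, or to within 2 patients at 0.5. This point does not alter it.

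**2. Precision, Study 1.** Suppose 10% of scans are missed independently at each follow-up time. Then 20 × 0.9² = 16.2 per arm have both follow-up scans and 20 × 0.9 = 18 have the 3-month scan.

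| Analysed per arm | Power, SD 0.5 | Power, SD 0.55 |
|---|---|---|
| 16 | 0.907 | 0.847 |
| 18 | 0.938 | 0.889 |

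This gap affects only an ANOVA on all three scans, and only when misses are intermittent. Under withdrawal, patients scanned at 3 months have normally also had the 4-week scan, and the gap largely disappears.

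**3. Bias in the 3-month between-arm difference, Study 1.** Suppose a fraction p of the treated arm is lost after the 4-week scan, and loss depends on the 4-week value. If exactly the lowest p are lost, the remaining patients' 3-month mean is too high by about [φ(z_p)/(1 − p)] × SD × correlation.
- p = 10%: 0.1755/0.9 = 0.195. Bias 0.195 × 0.5 × 0.3 = 0.029 to 0.195 × 0.5 × 0.7 = 0.068.
- p = 20%: 0.280/0.8 = 0.350. Bias 0.350 × 0.5 × 0.3 = 0.053 to 0.350 × 0.5 × 0.7 = 0.12.

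Simulations with 20 per arm agree. In the looser version, a patient's tendency to be lost has correlation 0.7 with the 4-week value, which multiplies the formula by 0.7.

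| Loss in treated arm | Complete cases, strict removal of lowest | Complete cases, looser dependence | Likelihood-based, largest absolute bias |
|---|---|---|---|
| 10% | +0.025 to +0.063 | +0.016 to +0.044 | 0.007 |
| 20% | +0.050 to +0.121 | +0.041 to +0.087 | 0.007 |

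For scale, the standard error with 20 against 16 patients is 0.5 × √(1/20 + 1/16) = 0.17. The likelihood-based estimate had a similar standard error to the complete-case one.

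**4. Change from baseline.** In the looser simulation, when loss depended on the 4-week scan, the complete-case difference in change was nearly unbiased (within 0.007), because baseline and 3-month values were given equal correlation with the 4-week value. When loss depended on the baseline scan it was biased by -0.02 to -0.08 at 10-20% loss, and the likelihood-based estimate stayed within 0.004.

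**5. Loss that depends on the unseen 3-month value (20%).** Complete-case bias in the 3-month difference was about +0.12; likelihood-based, +0.06 to +0.11. For change from baseline at correlation 0.5, with loss after the 4-week scan, the likelihood-based estimate was slightly worse (+0.08 against +0.06).

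**6. Study 2.** Difference detectable with 90% power from complete pairs: 3.2415 × 0.5 × √(2(1 − correlation))/√n. At correlation 0.5 this is 0.256 with 40 pairs and 0.287 with 32 (20% of pairs broken).

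**The case against.** Only the protocol is at hand. It says analysis of variance, not deletion of incomplete records, and handling of missing scans is commonly left to the SAP. That stands as a limit: the loss of incomplete records is how classical repeated-measures ANOVA behaves, not something the protocol states. But the protocol does choose the method, and the choice fits poorly with its own withdrawal rule.

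Several stronger readings are tempting, and the documents do not support them:
- **That every planned test drops anyone missing a scan.** A paired t-test needs two scans and an unpaired 3-month t-test needs one. Section 10.2.2 names both, so the 18 three-month scans in step 2 are already usable under the plan.
- **That the trial becomes underpowered.** At SD 0.5, 16 complete patients per arm still give 91% against a planned 90%. At SD 0.55 even 18 give 89%, so the shortfall there is not mainly due to the method.
- **That a bias of 0.12 should be expected.** It needs exactly the lowest 20% at 4 weeks to be lost, at correlation 0.7. The protocol lists side effects as reasons for stopping and nothing ties these to low uptake. Even 0.12 is less than one standard error.
- **That a mixed model cures the problem.** Steps 4 and 5 show where it helps and where it does not. A model with baseline only as a covariate would also drop a patient withdrawn before the 4-week scan, who has no outcome scan.
- **That Study 2 shares the asymmetry.** It has no untreated arm, and the documents give no stopping rates by drug.

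**Conclusion.** The point holds as a modest improvement to the analysis, not as an error in any stated figure. The protocol names methods that either need all three scans or leave baseline or 4-week information unused, while its 14-day rule can make loss differ by arm in Study 1 and can break pairs in Study 2.

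The effect on power is small. The bias avoided in the 3-month difference is roughly +0.02 to +0.12 mL/100 g/min, or 3% to 20% of the 0.6 target (0.02/0.6 and 0.12/0.6), with the looser dependence reaching about +0.09. This rests on assumed treated-arm loss of 10-20%, dependence on the 4-week scan, correlation 0.3-0.7 and SD 0.5. Removal of the bias holds under missing at random only. If loss is unrelated to uptake, there is no such bias to remove.

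**What to change.** In section 10.2.2, replace repeated-measures ANOVA with a linear mixed model fitted to all available scans, analysed by allocated arm.

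- **Study 1:** baseline, 4-week and 3-month scans all as outcomes; a common baseline mean across the three randomised arms, so that patients with only a baseline scan are retained; arm by visit; unstructured covariance; the baseline-adjusted 3-month contrast as the estimate. Healthy volunteers are not randomised and stay outside this constraint.
- **Study 2:** participant random effect with sequence, period and drug.
- **Both:** a sensitivity analysis in which missing values are allowed to differ from those predicted by the model, over a stated range.

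The cost is analysis wording and standard software, with no extra patients or scans and no change to the drug-stopping rule. The downside is reliance on missing at random. The model cannot recover scans never taken after withdrawal, which is why the sensitivity analysis belongs with it. The wording should be settled before outcome data are seen.
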